4.2 Toxicities and Dosing Delays/Dose Modifications

Any patient who receives treatment on this protocol will be evaluable for toxicity. Each patient will be assessed for the development of toxicity according to the Time and Events table (Section 5.5). Toxicity will be assessed according to the NCI Common Toxicity Criteria for Adverse Events (CTCAE), version 5.0. Dose adjustments should be made according to the system showing the greatest degree of toxicity.

Cabozantinib and pembrolizumab have class specific safety profiles based on their mechanism of action but may also cause AEs that overlap. For management of AEs which can be clearly attributed to cabozantinib or pembrolizumab, independent dose modification for either agent is allowed. Examples of VEGFR TKI associated AEs caused by cabozantinib are hypertension and hand-foot syndrome. Examples of immune-related AEs caused by pembrolizumab are pneumonitis and endocrinopathies. For AEs without clear attribution to either study treatment, management of toxicity should include dose modifications of both agents per the discretion of the investigator. Examples of overlapping AEs are diarrhea and transaminase increases.

Protocol #: UCI 18-124 MP 10/11//2022

Dose Modification Table

Dose Level	Agent	Dose
1 (starting dose)	Cabozantinib	40 mg
1 (starting dose)	Pembrolizumab	200 mg
-1 (50% reduction)	Cabozantinib	20 mg
-2	Cabozantinib	20 mg every other day

Toxicities:

Toxicity Dose Reductions			
NCI CTC Grade	Cabozantinib	Pembrolizumab	
Grade 0-2	No change from original starting dose	No change from original starting dose (unless described in 4.2.1)	
Intolerable grade 2 or grade 3	Hold until resolved to < Grade 1 then resume to dose level 1 or -1, depending on physician assessment	Hold until resolved to < Grade 2, then resume at dose level 1 (unless described in 4.2.1)	
Second episode of grade 3 or intolerable grade 2 first episode of grade 4 toxicity	Hold until resolved to ≤ Grade 1 then reduce to dose level one less than previous (i.e1 or -2) Discontinue permanently (unless investigator determines patient is deriving clear clinical benefit)	Discontinue permanently (unless described in 4.2.1)	
Third episode of grade 3	Remove subject from trial	Not applicable	

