4.3 Pembrolizumab adjustment for toxicity

No dosage reductions of pembrolizumab are recommended; treatment is withheld or discontinued to manage toxicities.

Colitis (immune-mediated):

Grade 2 or 3: Withhold pembrolizumab; administer corticosteroids (prednisone 1 to 2 mg/kg/day [or equivalent] followed by a taper); may resume upon recovery to grade 0 or 1 toxicity after corticosteroid taper.

Grade 4: Permanently discontinue pembrolizumab; administer corticosteroids (prednisone 1 to 2 mg/kg/day [or equivalent] followed by a taper).

Dermatologic toxicity (immune-mediated):

Grade 3 severe skin reactions or suspected Stevens-Johnson syndrome (SJS) or toxic epidermal necrolysis (TEN): Withhold pembrolizumab and refer for specialized care for assessment and treatment; may require corticosteroids (based on the severity).

Grade 4 severe skin reactions or confirmed SJS or TEN: Permanently discontinue pembrolizumab and refer for specialized care for assessment and treatment; may require corticosteroids (based on the severity).

Endocrinopathies (immune-mediated):

Grade 3 or 4: Withhold pembrolizumab until clinically stable.

Hyperglycemia, severe: Also administer antihyperglycemics.

Hyperthyroidism, severe (grade 3) or life-threatening (grade 4): Manage with thionamides and beta blockers as appropriate; may resume upon recovery to grade 0 or 1 toxicity or discontinue.

Hypophysitis, grade 2 (symptomatic): Also administer corticosteroids (followed by a taper) and hormone-replacement therapy if appropriate; may resume upon recovery to grade 0 or 1 toxicity or discontinue.

Hypophysitis, grade 3 or 4: Withhold or discontinue pembrolizumab (based on severity); also administer corticosteroids (followed by a taper) and hormone-replacement therapy as clinically indicated.

Nephritis (immune-mediated):

Grade 2: Withhold pembrolizumab; administer corticosteroids (prednisone 1 to 2 mg/kg/day [or equivalent] followed by a taper); may resume upon recovery to grade 0 or 1 toxicity after corticosteroid taper.

Grade 3 or 4: Permanently discontinue pembrolizumab; administer corticosteroids (prednisone 1 to 2 mg/kg/day [or equivalent] followed by a taper).

Pneumonitis (immune-mediated):

Grade 2: Withhold pembrolizumab; administer corticosteroids (prednisone 1 to 2 mg/kg/day [or equivalent] followed by a taper); may resume upon recovery to grade 0 or 1 toxicity after corticosteroid taper.

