Gastrointestinal perforation, GI fistula, and intra-abdominal and pelvic abscess: After starting treatment with cabozantinib, subjects should be monitored for early signs of GI perforation such as abdominal pain, nausea, emesis, constipation, and fever especially if known risk factors for developing GI perforation or fistula [37] are present. Discontinue cabozantinib and initiate appropriate management in subjects who have been diagnosed with GI perforation or fistula.

Diarrhea: Subjects should be instructed to notify their physician immediately at the first signs of poorly formed or loose stool or an increased frequency of bowel movements. Guidelines for the evaluation and management of diarrhea are shown in Table 9. Administration of antidiarrheal/antimotility agents is recommended at the first sign of diarrhea as initial management. Some subjects may require concomitant treatment with more than one antidiarrheal agent. When therapy with antidiarrheal agents does not control the diarrhea to tolerable levels, cabozantinib should be temporarily interrupted or dose reduced. When the diarrhea is controlled, retreatment with cabozantinib may be acceptable per investigator decision.

In addition, general supportive measures should be implemented such as continuous oral isotonic hydration, correction of fluid and electrolyte abnormalities, small frequent meals, and stopping lactose-containing products, high-fat meals, and alcohol.

Recurrent or prolonged diarrhea can be associated with anal or perianal skin erosions which increase the risk for anal abscesses, fistulas, or proctitis. Good personal hygiene should be emphasized. Regular examinations of the perianal region should be performed whenever diarrhea has occurred during treatment with cabozantinib. Infections of the perianal region should be treated per local guidelines.

Table 9: Management of Diarrhea Associated with Cabozantinib

Status	Management

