Tolerable Grade 1-2 (duration < 48 h)	 Continue with study treatment and consider dose reduction Initiate treatment with an antidiarrheal agent (eg, loperamide 4 mg followed by 2 mg after each episode of diarrhea [maximum: 16 mg loperamide per day]) Dietary modifications (eg, small lactose-free meals, bananas and rice) Intake of isotonic fluids (1-1.5 L/day) Re-assess after 24 hours: Diarrhea resolving to baseline bowel habits: gradually add solid foods and discontinue or decrease antidiarrheal treatment after 12 h diarrhea-free interval Diarrhea not resolving: Continue/resume antidiarrheal treatment
Intolerable Grade 2, Grade 2 > 48 h, or ≥ Grade 3	 Interrupt study treatment Ask subject to attend clinic Rule out infection (eg, stool sample for culture) Administer antibiotics as needed (eg, if fever or Grade 3-4 neutropenia persists > 24 h) Administer fluids (1-1.5 L/day orally or IV, as appropriate) for hydration or to correct electrolyte abnormalities For Grade 3-4 or complicated lower grade diarrhea consider hospitalization and IV hydration Re-assess after 24 h Diarrhea resolving to baseline bowel habits or Grade ≤ 1: consider restarting study treatment at reduced dose Diarrhea not resolving: Start and or continue antidiarrheal treatment (eg, loperamide 4 mg followed by 2 mg after each episode of diarrhea [maximum: 16 mg loperamide per day]). Consider starting second line antidiarrheal or referral to gastroenterologist

Nausea and vomiting: Antiemetic agents are recommended as clinically appropriate for treatment or prophylaxis of nausea and vomiting, along with supportive care. Dehydration and electrolyte abnormalities may be associated with vomiting and monitoring for and correction of fluid and electrolyte disturbances should be implemented. Antiemetic medications should be assessed for potential drug interactions (refer to Section 7.1.3 for further details).

Non-Gastrointestinal Fistula

Complications from radiation therapy especially of the thoracic cavity including mediastinum have been identified as a possible predisposing risk factor for non-GI fistula formation in subjects undergoing treatment with VEGF pathway inhibitors.

Discontinue cabozantinib and initiate appropriate management in subjects who have been diagnosed with a non GI fistula.

Hemorrhage

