	reduced dose if PPES recovers to Grade ≤ 1. Discontinue subject from
	study treatment if PPES does not improve within 6 weeks.

CTCAE, Common Terminology Criteria for Adverse Events; NSAID, non-steroidal anti-inflammatory drug; PPES, palmar plantar erythrodysesthesia syndrome.

Osteonecrosis

Refer to section 7.1.2

Proteinuria

Proteinuria has been reported with cabozantinib. Proteinuria should be monitored by measuring UPCR. Table 12 provides treatment guidelines for proteinuria deemed related to cabozantinib.

Cabozantinib should be discontinued in subjects who develop nephrotic syndrome (proteinuria > 3.5 grams per day in combination with low blood protein levels, high cholesterol levels, high triglyceride levels, and edema).

^a Permitted dose levels are defined by individual protocols.

Table 12: Management of Proteinuria Associated with	ssociated with Cabozantinib
---	-----------------------------

Severity of Proteinuria (UPCR)	Management of Proteinuria
≤ 1 mg/mg (≤ 113.1 mg/mmol)	No change in cabozantinib treatment or monitoring
> 1 and < 3.5 mg/mg (> 113.1 and < 395.9 mg/mmol)	 Consider confirming with a 24-h protein assessment within 7 days No change in cabozantinib treatment required if UPCR ≤ 2 mg/mg or urine protein ≤ 2 g/24 h on 24-h urine collection. Dose reduce or interrupt cabozantinib treatment if UPCR > 2 mg/mg on repeat UPCR testing or urine protein > 2 g/24 h on 24-h urine collection. Continue cabozantinib on a reduced dose if UPCR decreases to < 2 mg/mg. Consider interrupting cabozantinib treatment if UPCR remains > 2 mg/mg despite a dose reduction until UPCR decreases to < 2 mg/mg. Restart cabozantinib treatment at a reduced dose after a dose interruption. Repeat UPCR within 7 days and once per week. If UPCR < 1 mg/mg on 2 consecutive readings, UPCR monitoring can revert to protocolspecific times. (Second reading is confirmatory and can be done within 1 week of first reading.) If UPCR remains > 1 mg/mg and < 2 mg/mg for 1 month or is determined to be stable (< 20% change) for 1 month, check urine protein/creatinine per protocol or as clinically indicated.

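### Table 9 on diarrhea does not name the agent it acts on, allows restart after Grade 4 where the 4.2 table lists permanent discontinuation, and has no link to the colitis rules

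*Combined protocol and SAP*

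**What the plan says.** Five places in the protocol bear on diarrhea.

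- **4.2, text.** Each agent may be modified independently when an event is clearly attributable to it. When attribution is unclear, management should include modification of both, at the investigator's discretion. Diarrhea is in the second group: "Examples of overlapping AEs are diarrhea and transaminase increases".
- **4.2, toxicity table.** For a first Grade 4 toxicity it lists permanent discontinuation of each agent. Cabozantinib has an exception for clear clinical benefit. Pembrolizumab has an exception for whatever section 4.2.1 describes; no section 4.2.1 appears in the text supplied. The dose level table gives pembrolizumab a single level, 200 mg.
- **4.3.** "No dosage reductions of pembrolizumab are recommended; treatment is withheld or discontinued to manage toxicities". For immune-mediated colitis, pembrolizumab is withheld at Grade 2 or 3 with corticosteroids and may resume after a taper. At Grade 4 it is permanently discontinued.
- **4.4, diarrhea.** The introductory paragraph says that when antidiarrheal agents do not control the diarrhea, "cabozantinib should be temporarily interrupted or dose reduced". The table is headed "Table 9: Management of Diarrhea Associated with Cabozantinib". Its upper row covers "Intolerable Grade 2, Grade 2 > 48 h, or ≥ Grade 3". That row interrupts *study treatment*, asks the site to "Rule out infection (eg, stool sample for culture"), adds supportive care, and on recovery gives the step "Diarrhea resolving to baseline bowel habits or Grade ≤ 1: consider restarting study treatment at reduced dose".
- **7.1.2.** Under pembrolizumab, sites are told to monitor for colitis, to give systemic corticosteroids from Grade 2, and to investigate the cause once an immune-mediated event is suspected.

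**The concern.** Diarrhea is an event that the protocol itself says either drug may cause, and Table 9 is where an investigator is sent to evaluate and manage it. A site that follows the table meets an unnamed agent, a restart rule that covers Grade 4, and no prompt to consider an immune cause. A site that starts from the 4.2 table or from 4.3 meets different actions.

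What is at stake is that the same patient could be handled differently depending on which section is opened first, on a matter of safety. Departures from the protocol would also be hard to classify, because more than one action could be defended from the text.

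**Working it through.** No sample size, power or error rate is involved, so the check is a side-by-side reading.

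**Step 1. Which agent does Table 9 act on?** The section title, the table title and the introductory paragraph all point to cabozantinib. The cells say *study treatment*, and no cell in Table 9 names an agent. The usage around it points both ways. The hypertension text in 4.4 says *study treatment* where only cabozantinib is then modified, which favors the cabozantinib reading. The action cells of Tables 10 and 12, however, name cabozantinib, and the texts introducing those tables limit them to events deemed related to it. The sentence introducing Table 9 has no such limit. The term is therefore ambiguous here, with the weight of the context towards cabozantinib.

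**Step 2. Test each reading against the other rules.**

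| Point | If cabozantinib only | If both agents |
|---|---|---|
| Restart at a reduced dose | Possible: 4.2 gives levels -1 and -2 | Not possible for pembrolizumab: one level in 4.2, no reductions in 4.3 |
| Restart after Grade 4 | 4.2 lists permanent discontinuation unless there is clear benefit; Table 9 states no such condition | The cabozantinib conflict remains. In addition, 4.2 lists permanent pembrolizumab discontinuation (exception in the missing 4.2.1), and 4.3 requires it for Grade 4 immune-mediated colitis |
| Pembrolizumab when the cause is unclear | Table 9 is silent, while 4.2 calls for modification of both agents | Table 9 acts on it without the corticosteroid and taper steps that 4.3 sets for colitis |

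The Grade 4 row is the decisive one, because the difference is there on both readings.

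**Step 3. Table 9 against its own introduction.** The introductory paragraph offers interruption or dose reduction of cabozantinib. The upper row of the table offers interruption only.

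**Step 4. Route from Table 9 to the colitis rules.** Infection is the only cause the table asks the site to exclude. If the diarrhea does not resolve, the table continues antidiarrheals and then suggests a second-line agent or specialist referral. It has no step for immune-mediated colitis and no reference to 4.2, 4.3 or 7.1.2. In the other direction, the colitis entry in 4.3 applies once the event is labeled immune-mediated, and the duty in 7.1.2 to investigate the cause starts once that is suspected. Nothing in Table 9 prompts the suspicion.

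**Step 5. Table 11.** The Grade 3 entry for hand-foot syndrome begins by interrupting cabozantinib. Its last step removes the subject from "study treatment if PPES does not improve within 6 weeks". The change of term leaves it unclear whether pembrolizumab stops too.

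**The case against.** The strongest reply is that Table 9 concerns cabozantinib alone and so has no quarrel with 4.3. Its section, title and introduction say so, and a reduced dose can only mean cabozantinib because pembrolizumab has none. Table 9 and 4.3 also address differently labeled events, and nothing in Table 9 switches 4.3 off. The pembrolizumab column of the 4.2 table, 4.3 and 7.1.2 remain in force, and Table 9 itself provides for a clinic visit, possible hospitalization and specialist referral.

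Much of this stands. A reader might infer that Table 9 orders both agents to be interrupted and restarted, and so flatly contradicts 4.3. The documents do not support that: they nowhere say that *study treatment* in Table 9 means both drugs, and 4.3 governs once colitis is diagnosed. What remains is the Grade 4 difference from 4.2, which the cabozantinib reading does not remove, and the missing step between diarrhea of unclear cause and the colitis rules.

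It can also be said that Table 9 only asks the investigator to consider a restart, and that a finding of clear benefit would satisfy both places. That is true for patients with such a finding. For the others, 4.2 ends cabozantinib and Table 9 leaves restart open.

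Two further inferences should be resisted.

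- **Table 11 against 4.2.** A reader might infer a contradiction, since 4.2 gives hand-foot syndrome as an example of an event caused by cabozantinib. But 4.2 only permits independent modification, so stopping both agents would not breach it. The wording is unclear, no more.
- **Event rates as the size of the harm.** Section 7.1.4 lists diarrhea in 54% to 74% of cabozantinib patients (27 × 0.54 = 14.6 to 27 × 0.74 = 20.0 of 27) and colitis in 2% with pembrolizumab (1 − 0.98^27 = 0.42 chance of at least one case). These figures count events, including tolerable diarrhea during which treatment continues. They do not count events managed wrongly, and the protocol gives no rates for this combination at 40 mg.

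**Conclusion.** The point holds as an unreconciled set of instructions. Table 9 leaves the agent unnamed, differs from the 4.2 table on Grade 4 under either reading, differs from its own introduction on interruption versus reduction, and gives no route to 4.3 or 7.1.2 for an event that 4.2 calls overlapping. Sections 4.3 and 7.1.2 limit the risk but do not remove it, because they apply only once an immune cause is suspected or diagnosed.

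The size is qualitative: stated rules give different actions for the same patient on a safety matter. No effect on PFS-6, power or type I error is shown. It should be corrected, but it does not call the design into question.

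The conclusion rests on two assumptions. The first is that the permanent discontinuation entries in the 4.2 table belong to a first Grade 4 toxicity; that row is run together in the supplied text, and this is the natural reading. The second is that section 4.2.1 is absent from the protocol and was not merely lost from the supplied text. If it exists, it may settle the pembrolizumab part, but not the cabozantinib part.

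**What to change.** 1. In Table 9, replace *study treatment* with the agent or agents to which each step applies. Do the same in the last step of the Grade 3 entry in Table 11.
2. Reconcile the upper row of Table 9 with the Grade 4 entries in the 4.2 table and in 4.3, and with the introductory sentence on interruption or reduction.
3. Add to Table 9 a cross-reference to 4.2, 4.3 and 7.1.2 that states which section governs pembrolizumab when diarrhea is not clearly attributed to cabozantinib.
4. Supply section 4.2.1, or correct the references to it in the 4.2 table.

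Which clinical rule applies at each step is for the sponsor to decide; this review takes no view on it. The cost is an amendment to the wording of two tables, the references in the 4.2 table and one new cross-reference. The wording changes themselves require no added visits or tests and do not affect the sample size.

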3.2 Exclusion Criteria

- 3.2.1 Patients who have had chemotherapy within 2 weeks prior to entering the study
- 3.2.2 All toxicities attributed to prior anti-cancer therapy other than alopecia must have resolved to grade 1 or baseline
- 3.2.3 Patients may not be receiving any other investigational agents.
- 3.2.4 Patients with known brain metastases or cranial epidural disease unless accurately treated with radiotherapy and/or surgery (including radiosurgery) and stable for at least 4 weeks before first dose of study treatment. These individuals should be excluded from this clinical trial because of their poor prognosis and because they often develop progressive neurologic dysfunction that would confound the evaluation of neurologic and other adverse events. Eligible subjects must be neurologically asymptomatic and without corticosteroid treatment at the time of the first dose of study treatment.
- 3.2.5 History of allergic reactions attributed to compounds of similar chemical or biologic composition to pembrolizumab, cabozantinib_or other agents used in study. Patients with documented previous immune related toxicities which led to discontinuation of a checkpoint inhibitor.
- 3.2.6 Concomitant anticoagulation with oral anticoagulants (eg, warfarin), direct thrombin inhibitors (e.g., dabigatran), direct factor Xa inhibitors betrixaban, or platelet inhibitors (eg, clopidogrel).

 Allowed anticoagulants are the following:
 - a. Prophylactic use of low-dose aspirin for cardio-protection (per local applicable guidelines) and low-dose low molecular weight heparins (LMWH).
 - b. Therapeutic doses of LMWH or anticoagulation with direct factor Xa inhibitors rivaroxaban, edoxaban, or apixaban in subjects without known brain metastases who are on a stable dose of the anticoagulant for at least 1 week before first dose of study treatment without clinically significant hemorrhagic complications from the anticoagulation regimen or the tumor.
- 3.2.7 The subject has prothrombin time (PT)/INR or partial thromboplastin time (PTT) test ≥ 1.3 x the laboratory ULN within 7 days before the first dose of study treatment.
- 3.2.8 Uncontrolled intercurrent illness including, but not limited to, the following conditions:
 - a. ongoing or active infection
 - b. symptomatic congestive heart failure
 - uncontrolled hypertension defined as sustained blood pressure (BP) > 150 mm Hg systolic or > 100 mm Hg diastolic despite optimal antihypertensive treatment

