4.4 Cabozantinib adjustment for toxicity

The most frequent AEs experienced by ≥ 20% of subjects treated with cabozantinib in descending order of frequency were diarrhea, fatigue, decreased appetite, nausea, weight decreased, PPES, vomiting, constipation, hypertension, dysgeusia, dysphonia, asthenia, and dyspnea.

Subjects may also experience other medically important but less frequent AEs including arterial thrombotic AEs (e.g., deep vein thrombosis [DVT], pulmonary embolism, transient ischemic attack [TIA], and myocardial infarction [MI], severe hemorrhagic events, proteinuria, wound healing complications, gastrointestinal (GI) perforation, abscesses including intra-abdominal and pelvic abscess, GI and non-GI fistula formation, osteonecrosis, and reversible posterior leukoencephalopathy syndrome (RPLS).

Adverse events associated with laboratory abnormalities experienced by ≥ 5% of subjects treated with cabozantinib in descending order of frequency were anemia, AST increased, ALT increased, hypothyroidism, hypokalemia, hypomagnesemia, thrombocytopenia, hypocalcemia, hypophosphatemia, lactate dehydrogenase (LDH) increased, lipase increased, neutropenia, hyponatremia, ALP increased, hyponatremia, and leukopenia.

Many adverse events may occur early (within the first few weeks) in the course of treatment with cabozantinib, as cabozantinib is expected to reach steady state exposure at approximately 2 weeks following first dose. Events that generally have an early onset include hypocalcemia, hypokalemia, thrombocytopenia, hypertension, PPES, abdominal pain, mucosal inflammation, constipation, diarrhea, and vomiting.

Adverse events should be managed with supportive care at the earliest signs of toxicity. Dose reductions and treatment interruptions should be considered. Dose reductions are recommended for events that, if persistent, could become serious or intolerable (Section 4.2).

Cabozantinib should be discontinued for the following AEs: visceral perforation or fistula formation, severe hemorrhage, serious arterial thromboembolic events, nephrotic syndrome, hypertensive emergency, persistent uncontrolled hypertension despite optimal medical management, and reversible posterior leukoencephalopathy syndrome (RPLS).

Gastrocintestinal Disorders

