Hemorrhagic events, including serious and sometimes fatal events, have been reported with cabozantinib. Subjects should be monitored for bleeding events with serial complete blood counts and physical examination while on study. The risk of hemorrhage in cabozantinib-treated subjects with brain metastases has not been thoroughly analyzed. Subjects enrolled with treated and stable brain metastases should be monitored with a high index of suspicion if symptoms that could be due to a CNS hemorrhage occur.

Cabozantinib should be discontinued in subjects with serious and life-threatening bleeding events or recent hemoptysis (≥ 2.5 mL of red blood).

Thromboembolic events

Refer to section 7.1.2

Hypertension

Table 10 provides treatment guidelines for hypertension deemed related to cabozantinib. Blood pressure should be monitored in a constant position visit to visit, either sitting or supine in a relaxed setting. Decisions to reduce or interrupt the dose of study treatment must be based on BP readings taken by a medical professional and must be confirmed with a second measurement at least 5 minutes following the first measurement.

Cabozantinib should be discontinued in subjects with hypertensive emergency.

Table 10: Management of Hypertension Associated with Cabozantinib

Criteria for Dose Modifications	Treatment/Cabozantinib Dose Modification				
Subjects NOT receiving optimized anti-hypertensive therapy					
> 150 mm Hg (systolic) ^a and < 160 mm Hg OR > 100 mm Hg (diastolic) and < 110 mm Hg	 Optimize antihypertensive medications by adding new or additional antihypertensive medications and/or increase dose of existing medications. Reduce cabozantinib treatment by one dose level if optimal antihypertensive therapy (usually to include 3 agents) does not result in BP <150 mm Hg systolic or <100 mm Hg diastolic If subject is symptomatic interrupt cabozantinib treatment 				

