≥ 160 mm Hg (systolic) OR ≥ 110 mm Hg (diastolic)	 Reduce cabozantinib by one dose level^b or interrupt cabozantinib treatment per investigator discretion Add new or additional anti-hypertensive medications and/or increase dose of existing medications and monitor subject closely for hypotension. If optimized antihypertensive therapy (usually to include 3 agents) does not result in BP < 150 mm Hg systolic or < 100 mm Hg diastolic, cabozantinib treatment should be dose reduced further or interrupted Cabozantinib treatment should be dose interrupted if upper limits of systolic BP (≥ 160 mm Hg) are sustained and not adequately manageable or if systolic BP is > 180 mm Hg or diastolic BP > 110 mm Hg, or if subject is symptomatic Re-start cabozantinib treatment at the most tolerable dose and re-escalate only if BP falls to and is sustained at < 150 mm Hg systolic and < 100 mm Hg diastolic 				
Hypertensive emergency ^c	Discontinue cabozantinib treatment				

BP, blood pressure.

- ^a The investigator may decide to initiate or adjust antihypertensive treatment at a lower threshold than systolic BP >150 or diastolic BP >100 based on their clinical judgment and assessment of the individual subject.
- ^b Permitted dose levels are defined by individual protocols.
- ^c Hypertensive emergency is defined as uncontrolled elevated BP with clinical evidence of progressive or impending end-organ damage (eg, myocardial infarction/ischemia, intracranial hemorrhage, cerebral ischemia, pulmonary edema, encephalopathy, kidney damage).

CONFIDENTIAL

Stomatitis and Mucositis

Preventive measures may include a comprehensive oral examination to identify and treat any potential risk for complications before study treatment is initiated. Appropriate correction of local factors should be instituted as indicated, such as modification of ill-fitting dentures and appropriate care of gingivitis. During treatment with cabozantinib, good oral hygiene and standard local treatments such as non-traumatic and non-irritating cleansing, and oral rinses (eg, with a weak solution of salt and baking soda) should be maintained. Lips should be kept moisturized with lip balm. The use of lipstick, lip-gloss, and Vaseline should be avoided.

Local treatment should be instituted at the earliest onset of symptoms. Obtain bacterial/viral culture if oral infection is suspected and treat infection as clinically indicated.

Skin and Subcutaneous Tissue Disorders

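### Table 10 joins its blood-pressure control target with 'or', so isolated systolic 151–159 or isolated diastolic 101–109 mm Hg on optimal therapy reads as controlled and triggers no cabozantinib dose step

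*Combined protocol and SAP*

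**What the plan says.** Table 10 in section 4.4 gives the blood pressures at which cabozantinib is reduced or interrupted.

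- **Row 1** is entered when systolic is above 150 and below 160, "OR > 100 mm Hg (diastolic) and < 110 mm Hg". Its second bullet lowers cabozantinib by one level if optimal therapy, usually three agents, "does not result in BP <150 mm Hg systolic or <100 mm Hg diastolic". Its last bullet interrupts treatment if the patient has symptoms.
- **Row 2** is entered at systolic 160 or more, or diastolic 110 or more. The first step has no condition: reduce one level "or interrupt cabozantinib treatment per investigator discretion". The third bullet adds that if optimized therapy "does not result in BP < 150 mm Hg systolic or < 100 mm Hg diastolic, cabozantinib treatment should be dose reduced further or interrupted". A separate bullet interrupts for sustained and unmanageable systolic of 160 or more, systolic above 180, diastolic above 110, or symptoms. After a restart, the investigator may "re-escalate only if BP falls to and is sustained at < 150 mm Hg systolic and < 100 mm Hg diastolic".

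Elsewhere, exclusion 3.2.8 bars patients with "uncontrolled hypertension defined as sustained blood pressure (BP) > 150 mm Hg systolic or > 100 mm Hg diastolic despite optimal antihypertensive treatment". The discontinuation list in section 4.4 includes "persistent uncontrolled hypertension despite optimal medical management". Section 7.1.2 withholds cabozantinib when hypertension remains uncontrolled under suitable management. Neither of these last two texts attaches a number to 'uncontrolled'.

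**The concern.** A rule that acts when therapy fails to reach 'A or B' acts, taken literally, only when both A and B are missed. With A as systolic below 150 and B as diastolic below 100, a patient whose systolic stays at 158 is treated as controlled as long as diastolic is under 100. The rest of the protocol treats either raised component as a problem.

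What is at stake is patient safety and uniform dosing. Section 4.4 requires decisions to reduce or interrupt to rest on measured and confirmed readings, so these thresholds are meant to be used. In row 1, an investigator who reads the bullet literally leaves the dose alone, and one who reads it as 'both below' steps down. From the starting dose that step is 40 mg to 20 mg (section 4.2), so the same patient could receive doses that differ twofold.

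**Working it through.** The plan states no figure to reproduce here. The check is of the rule's logic, with S for systolic and D for diastolic in mm Hg.

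**1. Inputs** (section 4.4 Table 10, and 3.2.8)
- Target in row 1 second bullet and row 2 third bullet: S < 150 or D < 100.
- Re-escalation target: S < 150 and D < 100.
- Row 1 entry: 150 < S < 160, or 100 < D < 110.
- Row 2 entry: S ≥ 160 or D ≥ 110.
- Uncontrolled under 3.2.8: S > 150 or D > 100, sustained on optimal treatment.

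**2. When the step is triggered**
- As written: not (S < 150 or D < 100), which is S ≥ 150 **and** D ≥ 100.
- With 'and' in the target: not (S < 150 and D < 100), which is S ≥ 150 **or** D ≥ 100.

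**3. Test readings**, taken as sustained on optimal therapy without symptoms

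| Reading | Target met with 'or' | Target met with 'and' | Beyond 3.2.8 limits | Row 2 entry |
|---|---|---|---|---|
| 158/90 | yes | no | yes | no |
| 145/105 | yes | no | yes | no |
| 158/105 | no | no | yes | no |
| 148/98 | yes | yes | no | no |
| 150/90 | yes | no | no | no |
| 165/90 | yes | no | yes | yes |
| 149/110 | yes | no | yes | yes |

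The first two rows are the defect: row 1 admits both readings, 3.2.8 would call both uncontrolled, and the target as written calls both controlled. At 158/105 both wordings trigger the step, and at 148/98 neither does. At 165/90 and 149/110 the wordings differ, but row 2 entry already acts.

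**4. The band.** Step through whole-number readings: S 150–159 with D 70–99 gives 10 × 30 = 300 pairs, and D 100–109 with S 120–149 gives 30 × 10 = 300 pairs. As written, 0 of these 600 trigger the step. With 'and', all 600 do. Exactly 150 or exactly 100 meets neither row 1 entry nor 3.2.8, because both use a strict inequality. The contradiction therefore starts at 151 or 101 and covers 9 × 30 + 9 × 30 = 540 of the 600 pairs. These counts describe the rule. They say nothing about how often patients have such readings.

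**5. Other numeric rules in Table 10.** Row 2's interruption bullet needs sustained S of at least 160, S above 180, D above 110, or symptoms. None applies to an asymptomatic reading in the band. Footnote a allows antihypertensive treatment to be started or adjusted at lower pressures, but does not address the cabozantinib dose.

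**6. What is lost in each row.** In row 1 the one-level reduction, its only dose step for an asymptomatic patient, is not triggered. In row 2 a reduction or interruption has already happened, so only the further step is lost.

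**The case against.** The strongest reply is that nobody would apply the literal reading. A patient who enters row 1 at 158/90 has diastolic below 100 before any drug is added. The target would be met on entry, and the reduction could never apply to an isolated elevation that the row is written to admit. In ordinary English, failing to reach one goal or the other can mean that either was missed. The entry criteria, the re-escalation bullet and 3.2.8 all point the same way.

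The reply also has other text behind it:
- Section 4.4 opens by advising that reductions and interruptions be considered, and it recommends reductions for events that could become serious or intolerable if they persist.
- The same section discontinues for persistent uncontrolled hypertension, section 7.1.2 withholds for it, and Table 10 interrupts for symptoms.
- The general dose table in section 4.2 acts on grade 3 or intolerable grade 2 toxicity.
- Table 10 is presented as treatment guidelines and worded with 'should'.

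Much of this stands. The intended meaning can be recovered, and silence in Table 10 is not an instruction to keep the dose. That makes the severity low. It does not make the wording correct. The row 2 cell uses 'and' where it plainly means both, so a careful reader could take 'or' as deliberate. The general advice has no threshold. The 4.4 list and 7.1.2 leave 'uncontrolled' undefined. If the 3.2.8 definition is carried over to them, a patient at 158/90 is withheld under 7.1.2 and, if it persists, discontinued under 4.4, while Table 10 read literally asks for nothing. The CTCAE hypertension grades are not reproduced in the documents, so the overlap of the section 4.2 table with this band cannot be settled from them.

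**Conclusion.** The point holds as a minor wording error in a dose-modification rule that investigators will use. It affects asymptomatic patients on optimal therapy with isolated systolic 151–159 (diastolic below 100) or isolated diastolic 101–109 (systolic below 150). It rests on the literal reading of 'or' and on no outside data.

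Three stronger readings are tempting, and the documents support none of them:
- **Such patients are left unprotected or must stay on full dose.** The texts listed under the objection still allow or require action, and a row 2 patient has already been reduced or interrupted.
- **A known share of patients is affected.** Section 7.1.4 lists hypertension in 30% to 61% of patients on cabozantinib. If that held at 40 mg, an assumption, 0.30 × 27 = 8.1 to 0.61 × 27 = 16.5 patients would have hypertension of any degree. That is only the pool to which Table 10 could apply. The documents give no rate for this band on optimal therapy, so no count can be given.
- **The trial's conclusions are at risk.** PFS-6, the sample size and the error rates in section 9 make no use of the Table 10 target and are unaffected.

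**What to change.** In Table 10, row 1 second bullet and row 2 third bullet, replace 'or' with 'and' between the systolic and diastolic limits. The target is then met only when both components are below their limits, as the re-escalation bullet in the same table already requires. No new threshold or time limit is needed.

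The cost is two one-word edits at the next amendment, with no added visits, measurements or patients.
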